Inclusion criteria for this study are: 1) over the age of 18, 2) speak either English or Spanish, 3) ability to provide informed consent, 4) currently enrolled in the SSP and have exchanged at least two times in the past three months, 5) have a negative HIV rapid test result, 6) estimated creatinine clearance > 30 ml/minute for Descovy and >60 for Truvada. Individuals will be excluded from this study if they 1) do not meet the above criteria of inclusion, 2) decline to participate, 3) test positive for HIV via rapid test, 4) are pregnant or plan on becoming pregnant 5) have symptoms acute HIV. *Any other comorbidities that at the discretion of the investigator would prevent the participant from participating in the study.*

5) Study Design

To create a sustainable protocol for dissemination of our *Rapid Mobile PrEP* initiation at future Florida SSP expansion sites (Aim 1):

Firstly, we will develop a protocol for initiation of *Rapid Mobile PrEP* at the Miami IDEA SSP site. Throughout the grant period, we will continuously update our protocol through rapid feedback and implementation of new approaches to overcome encountered problems as they arise. In addition to academic dissemination of our work, we will produce an adaptable protocol for new SSPs as they expand throughout the state. We will enroll a prospective, open-label cohort, similar to the PrEP Demonstration Project at the Miami-Dade County Health Department, assessing uptake, adherence, and retention.

Acceptability and feasibility of *Rapid Mobile PrEP* among SSP clients (Aim 2):

We will pilot test mobile PrEP at the IDEA SSP (N=100), conducting ongoing brief qualitative assessments and process improvement and developing sustainable protocol for adaptation at Florida's SSP expansion sites in geographic hotspots. We will report the proportion of eligible PWID who elect to initiate *Rapid Mobile PrEP* to understand acceptability among at-risk PWID. Likewise, we will report correlates of initiation and retention. We hypothesize that coupling PrEP services with the provision of syringes and harm reduction equipment will increase retention in this *Rapid Mobile PrEP* initiation study.

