We will conduct detailed interviews including demographics, drug and sexual risk behaviors, and medical history. Labs will include: HIV via 4th generation test, HBsAg, gonorrhea/chlamydia (urine, rectal, pharyngeal), syphilis, creatinine, and HCV RNA. Participants will be offered immediate FTAf at the IDEA SSP on the first encounter and will meet with the peer navigator for a medication management and adherence plan that may include on-site storage of medications and deliveries of PrEP coupled with provision of injection supplies.

If a participant becomes ineligible for PrEP during follow up based on renal function, other adverse events, or HIV infection, they will be contacted and discontinued from the study. Participants who test positive for HIV during study follow up will be linked to HIV care. Participants with chronic hepatitis B virus infection will be contacted immediately by the clinician for a discussion of the risks and benefits of FTAf in the context of chronic hepatitis B. Finally, PWID who decline study enrollment will be asked to participate in a brief survey that will include demographics, reason for declining, PrEP awareness and knowledge, and perceived HIV risk. Those who decline the study will receive \$25 cash payment for this brief, 30 minute interview.

[figure not shown]
The effectiveness of PrEP requires that it be taken every day minimizing missed doses as well as continuing PrEP over time during periods of potential HIV exposure. Follow up visits will occur at 1, 3, 6, 9 and 12 months. At each study visit participants will complete surveys about PrEP use since their last visit including semiqualitative/open-ended questions about reasons for use or non-use. We will use this combination of quantitative and qualitative data to determine individual and structural contributors to non-adherence and discontinuation of PrEP among PWID. For each study visit including baseline, participants will receive \$50 cash payment.

6) Arms and Interventions

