This single arm pilot study will assess the effectiveness of on site initiation of PrEP and followup at an SSP (fixed site or mobile exchange on outreach). The study is 1 year duration, and study visits are conducted at 0, 1, 3, 6, 9 and 12 months as outlined above. The intervention is delivery of PrEP outside of a traditional healthcare clinic. The principal medication offered will be FTAF 200/25mg tablet to be administered orally. In this study, we will offer Descovy to men and trans women due to decreased risk of side effects. If the participant is assigned female at birth, Truvada will be prescribed instead of study drug per FDA approval. **It is noted that significant risk for HIV among PWID is sexual.** The intervention will include wraparound support by the peer navigator. Study visits will be conducted either at the IDEA Exchange fixed location, or on the mobile unit in the community (e.g. homeless encampments). The fixed site and mobile unit are equipped with private rooms for medical encounters. Medical visit with a provider and phlebotomy will be provided on site.

7) Procedures Involved*

Figure 1. Conceptual Framework for *Rapid Mobile PrEP*

8) Primary Endpoints

| Patient-Level Outcomes | Definition | Implementation Construct Domain | Definition |
|--|---|---|--|
| PrEP levels at 6 month follow up (primary) | Intracellular levels of tenofovir diphosphate (TFV-DP) by dried blood spot (DBS). | Acceptability/feasibility of Rapid Initiation of PrEP | Number of PWID at risk for HIV that enter Rapid Mobile PrEP |
| Time to PrEP initiation post negative HIV | Number of days between receiving negative HIV test | Acceptability/feasibility of Rapid Initiation of PrEP | Mean time to PrEP initiation among PWID. |

| | | | |
|------------------------|---|-------------------------|---|
| rapid test (secondary) | result and initiating PrEP, by self-report | | |
| PrEP Persistence | TFV-DP levels on DBS, pill counts, medication log, appointment attendance | Barriers to persistence | Exploration of challenges to PrEP persistence |

9) Data and Specimen Banking*

For clinical data, we will use the UHealth's electronic health record, UChart, which is locked under dual authentication.

All data collected will be housed in the REDCap database system, which is locked under dual authentication by University of Miami Information Technology and then extracted for analysis by the principal investigator. Only study staff will have access to survey results.

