Study Drug: Serious risks of taking Truvada and Descovy includes serious drug reactions such as lactic acidosis, hepatomegaly with steatosis, hepatotoxicity, hepatitis B virus exacerbation, pancreatitis, nephrotoxicity, bone density loss, neutropenia, immune reconstitution syndrome, autoimmune disorders and angioedema. Common adverse reactions include diarrhea, headache, fatigue, elevated CK, abnormal dreams, dizziness, insomnia, hypercholesterolemia, hyperamylasemia, neutropenia, LFTs elevated, nausea/vomiting, depression, rash, dyspepsia, abdominal pain, asthenia, increased creatinine, arthralgia/myalgia, cough, paresthesia, peripheral neuropathy, palmar-plantar hyperpigmentation, hypertriglyceridemia, hematuria, hyperglycemia, glycosuria, rhinitis and flatulence.

Risk of HIV acquisition in PWID is extremely complex. This study is to assess the acceptability on on-site initiation of PrEP and persistence over 1 year. Importantly, Descovy is preferred for PrEP due to decreased nephrotoxicity and bone toxicity. However, the initial studies were only in men who have sex with men and transwomen. Therefore, we will prescribe Descovy, the preferred medication to those who meet eligibility i.e. MSM or transwomen. We will prescribe Truvada to cis women while explaining the increased risk of loss of bone mineral density and renal function. Importantly, HIV outbreaks in this country among PWID, including in Miami, and their resultant investigations have all indicated that sexual risk, especially from sex work, plays a major role in HIV acquisition. Therefore we will offer different PrEP medications only because the studies for Descovy have not yet been conducted in women.

12) Adverse Events and Serious Adverse Events

AEs will be any of the common adverse reactions defined above. SAEs will include any hospitalization or death or disability that occurs with participants in the trial. AEs will be reported to the IRB in continuing reviews. SAEs will be reported to the IRB within 24 hours.

The following AEs of interest will be collected and reported: lactic acidosis, hepatomegaly with steatosis, hepatotoxicity, hepatitis B virus exacerbation, pancreatitis, nephrotoxicity, neutropenia, immune reconstitution syndrome, autoimmune disorders and angioedema.

13) Potential Benefits to Subjects*

The potential benefit to the PWID is that they will be able to access rapid on-site PrEP initiation with few barriers, improving their overall health in the short and long term.

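### The AE definition has no onset-or-worsening rule and no structured baseline symptom record is described, so pre-existing complaints can be reported as AEs in this single-arm study

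*Combined protocol and SAP*

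**What the plan says.** Section 12 gives the definition in one sentence: "AEs will be any of the common adverse reactions defined above". This points back to Section 11, where the list begins "Common adverse reactions include diarrhea, headache, fatigue, elevated CK, abnormal dreams, dizziness, insomnia" and continues to 29 terms. No condition on onset, worsening, severity or relatedness is attached. The companion sentence for serious events, "SAEs will include any hospitalization or death or disability that occurs with participants in the trial", refers to being in the trial and not to the first dose. On reporting, Section 12 says "AEs will be reported to the IRB in continuing reviews". A second paragraph of Section 12 names ten AEs of interest that are also to be collected and reported.

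On baseline information, Section 5 says "We will conduct detailed interviews including demographics, drug and sexual risk behaviors, and medical history" and "Labs will include: HIV via 4th generation test, HBsAg, gonorrhea/chlamydia (urine, rectal, pharyngeal), syphilis, creatinine, and HCV RNA". Section 4 lists among the exclusions "5) have symptoms acute HIV". Section 6 adds an on-site visit with a provider and does not say what it covers. Section 6 also sets the design: "This single arm pilot study will assess the effectiveness of on site initiation of PrEP".

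**The concern.** An AE count is meant to describe what happens after treatment starts. A definition that rests only on whether a term is on a list does not separate a headache or a spell of insomnia that began after the first dose from one that was there before it. In a randomised trial the control arm would show the background level. Here there is no control arm, so each participant's own pre-dose state is the nearest available reference.

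The window for recording that state is short, because Section 5 offers PrEP at the first encounter. Symptoms not written down then cannot be reliably reconstructed later. At stake is whether the AE reports to the IRB, and any later account of tolerability in this population, can be read as events arising on PrEP.

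**Working it through.** **No figure to reproduce.** The documents state no AE rate, symptom prevalence or AE analysis. The check is therefore a reading of the text, followed by an illustration on assumed inputs.

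**Step 1: what the list contains.** Counting the Section 11 terms gives 29. Ten are laboratory findings: elevated CK, hypercholesterolemia, hyperamylasemia, neutropenia, raised LFTs, increased creatinine, hypertriglyceridemia, hematuria, hyperglycemia and glycosuria. The other 29 − 10 = 19 are symptoms or clinical findings. Of these, headache, fatigue, dizziness, insomnia, nausea/vomiting, depression, abdominal pain, cough and rhinitis are plainly non-specific.

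**Step 2: what baseline information could be set against it.**

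| Source | What it gives | Matched to the AE list? |
|---|---|---|
| Interview (Section 5) | Medical history | Not stated |
| Laboratory tests (Section 5) | Creatinine is the only test corresponding to one of the ten laboratory terms | One term |
| Exclusion (Section 4) | Some current symptoms must be asked about | Not stated |
| Provider visit (Section 6) | Content unspecified | Not stated |

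Baseline is not blank, but no source is described as a record of the listed symptoms, and no comparison of follow-up events with baseline is planned.

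**Step 3: direction and possible size for one symptom.** All inputs here are assumptions; none comes from the documents. Let q be the share with the complaint before the first dose, t the share of the rest who newly develop it, and f the fraction of pre-existing complaints that staff report as AEs. Ignoring worsening:

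- share reported = f·q + (1 − q)·t
- share with new onset = (1 − q)·t

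On a fully literal reading f = 1. If staff informally exclude pre-existing complaints, f = 0. Per 100 participants, the planned number:

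| q | t | Reported, f = 1 | New onset (f = 0) | Pre-existing share, f = 1 |
|---|---|---|---|---|
| 5% | 2% | 6.9 | 1.9 | 72% |
| 5% | 10% | 14.5 | 9.5 | 34% |
| 20% | 5% | 24.0 | 4.0 | 83% |
| 40% | 2% | 41.2 | 1.2 | 97% |
| 40% | 10% | 46.0 | 6.0 | 87% |

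For the middle row: 0.20 + 0.80 × 0.05 = 0.24 against 0.80 × 0.05 = 0.04, and 0.20 / 0.24 = 83%. The direction is fixed, since f·q is never negative. The size depends on q, t and f, and the documents settle none of them.

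**The case against.** The strongest reply is that the wording already implies a link to the drug. The definition speaks of reactions, the list sits under the study-drug heading of Section 11, and some entries, such as increased creatinine, imply a change. Section 5 also mentions AEs in the context of follow-up. A sensible site team may leave pre-existing complaints out. This stands, and it is why the point is that such complaints can be counted. A reader might infer that they will be, but the text does not support that. Equally, no written rule keeps them out, and a chronic complaint mentioned at month 1 is also a follow-up report.

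A reader might also infer that current symptoms go unrecorded at baseline. The documents do not show that. The interview contents are introduced as inclusive, entry requires some symptom screening, and clinical data are kept in the electronic health record (Section 9). The procedures figure in Section 7 is not shown and some text was removed, so absence cannot be confirmed. What stands is that no structured record tied to the AE list is described.

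The consequence is limited. AEs are not among the Section 8 endpoints, Section 10 plans no AE analysis, and none of the ten AEs of interest in Section 12 is one of the non-specific complaints listed above. This stands in full.

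**Conclusion.** The point holds as a modest improvement to safety recording. Section 12 lacks an onset-or-worsening criterion, and the available text describes no structured baseline symptom record, so pre-existing non-specific complaints can be reported as AEs in an uncontrolled study. Any resulting error inflates the AE description given to the IRB. It does not reach the primary endpoint, and no planned estimate is biased.

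The size cannot be derived from the documents. The table under the check shows only how the count behaves under assumed inputs. Two stronger readings should be resisted:

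- **A share of participants with at least one spurious AE.** Multiplying assumed prevalences across several symptoms needs figures the documents do not give, and independence that is implausible if the complaints occur together.
- **Background complaints ending PrEP or study participation.** The Section 5 rule turns on a participant losing eligibility for PrEP during follow-up. Nothing in the text says that the mere presence of a listed symptom does this.

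**What to change.** 1. At month 0, before the first dose, complete the listed symptoms as a short yes/no and severity checklist within the existing REDCap interview. If such a record already exists in the procedures or the medical visit, cite it in Section 12 and use it.
2. In Section 12, define an AE as a listed event that starts or worsens after the first dose, and record the onset date and the clinician's relatedness judgement.
3. In reports, give new or worsened events as the main count, with baseline prevalence of each symptom beside it.

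The cost is one checklist, one definition sentence and a few minutes per participant; no treatment rule changes. The remedy is partial. A complaint that comes and goes may be absent at month 0 and appear later for reasons unrelated to PrEP, and it would still count as new. The baseline figure and the relatedness judgement reduce that ambiguity but cannot replace a control arm.

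### Section 12 limits adverse events to a list of known common reactions, so an unlisted event without hospitalization, death or disability has no required recording or reporting route

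*Combined protocol and SAP*

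**What the plan says.** Section 11 (Risks to Subjects) gives two lists for Truvada and Descovy. The list of serious risks includes "pancreatitis, nephrotoxicity, bone density loss, neutropenia, immune reconstitution syndrome, autoimmune disorders and angioedema". The list of common reactions opens "Common adverse reactions include diarrhea, headache, fatigue, elevated CK, abnormal dreams, dizziness, insomnia".

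Section 12 (Adverse Events and Serious Adverse Events) then sets three rules:

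- AEs: "AEs will be any of the common adverse reactions defined above". They go to the IRB at continuing review.
- SAEs: "SAEs will include any hospitalization or death or disability that occurs with participants in the trial". They go to the IRB within 24 hours.
- AEs of interest: "The following AEs of interest will be collected and reported: lactic acidosis, hepatomegaly with steatosis", and so on through the serious-risk list. No timeline is attached to these.

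Section 5 (Study Design) uses the term once more. A participant may become ineligible for PrEP and be discontinued "based on renal function, other adverse events, or HIV infection".

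**The concern.** An AE definition normally starts from anything untoward that happens to a participant and leaves relatedness and expectedness for later judgement. Here the definition starts from what is already known about the drugs. A new or unlisted harm is then not an AE, however often it occurs, unless it reaches one of the three SAE outcomes.

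Three features of the plan make this more than a drafting preference.

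- Section 3 describes PrEP as little studied in people who inject drugs, and Section 11 says the initial Descovy studies were confined to men who have sex with men and transwomen. Prior lists are least reliable in such a setting.
- Section 6 places visits at the exchange's fixed site or on a mobile unit in the community, so a serious event managed on site without admission is foreseeable.
- Section 5 intends the protocol to be adapted by other Florida programs, so the definition could be copied with it.

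At stake are participant protection and the completeness of AE reports to the IRB.

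**Working it through.** No sample size, power or error-rate figure is involved, and the plan states no number to reproduce. The check compares the term lists in Sections 11 and 12 and then reads the SAE sentence against them.

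**Counts, taking each listed term once**

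| List | Where | Terms |
|---|---|---|
| Serious risks | Section 11 | 11 |
| Common reactions (the AE definition) | Section 11, via Section 12 | 29 |
| AEs of interest | Section 12 | 10 |

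**Overlaps**

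1. AEs of interest that are also common reactions: 1 (neutropenia). So 10 − 1 = 9 AEs of interest are not AEs under the definition that precedes them.
2. Distinct terms named for collection: 29 + 10 − 1 = 38.
3. Serious risks carried into the AEs of interest: 10 of 11. In Section 11 the sequence runs "pancreatitis, nephrotoxicity, bone density loss, neutropenia". In Section 12 neutropenia follows directly on nephrotoxicity, so bone density loss has dropped out.
4. Bone density loss is not among the 29 common reactions either (the nearest term is arthralgia/myalgia). It is the only one of the 11 serious risks in neither list. Yet Section 11 gives lower bone toxicity as a reason for preferring Descovy, and says the bone risk will be explained to cis women prescribed Truvada.

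The match is term by term. Some pairs are close in meaning: raised liver tests and hepatotoxicity, raised creatinine and nephrotoxicity, hyperamylasemia and pancreatitis. If those three pairs were treated as the same event, 9 − 3 = 6 AEs of interest would still lie outside the definition.

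**Where an event goes under the rules as written**

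| Event | Hospitalization, death or disability | None of these |
|---|---|---|
| On the common-reaction list | SAE, 24 hours | AE, continuing review |
| AE of interest only | SAE, 24 hours | Collected and reported, no timeline stated |
| On neither list | SAE, 24 hours | No stated route |

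The gap is the bottom right cell. It holds every unlisted event short of the three outcomes. That includes an unlisted life-threatening event resolved on site, such as an overdose reversed without admission, and a bone event without admission or disability. A listed life-threatening event treated on site, such as angioedema, is collected, but the SAE sentence does not bring it under 24-hour reporting.

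**The case against.** The SAE sentence is broad in one important respect: it has no list and no relatedness test. Any harm that leads to hospitalization, death or disability is reported, expected or not. A reader might infer from the AE sentence that the trial cannot detect an unexpected harm at all, or that no life-threatening event without admission is captured. The documents do not support either reading. The SAE sentence catches the first group when one of its outcomes occurs, and the AE-of-interest list catches listed events such as lactic acidosis, pancreatitis and angioedema whether or not the participant is admitted.

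The SAE sentence and the introduction to the common reactions both use the verb *include*, which can be read as non-exhaustive. For SAEs this has some force. For AEs it helps less: even if the common list is illustrative, the definition still admits only common adverse reactions, and so excludes an event that is neither common nor known.

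The plan claims no safety endpoint. Its aims are a sustainable protocol, acceptability and feasibility, and its endpoints in Section 8 are drug levels, time to initiation and persistence. That stands. The point rests on participant protection and on what the IRB is told, not on a biased safety estimate.

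The text available schedules no bone imaging, so restoring the bare term bone density loss would capture little. That also stands, and it is why the fix asks for clinically recognised events.

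Events may still be noted in the electronic health record (Section 9), so the claim is that Section 12 does not require AE recording, not that no trace would exist. Some text after Section 13 was not available for this review. Section 12 is complete, and any safety text elsewhere would have to be reconciled with it.

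**Conclusion.** The point holds for a defined class of events: those on neither list that do not lead to hospitalization, death or disability. For these, Section 12 as written requires neither recording as an AE nor reporting to the IRB, so AE reports would be incomplete. Two internal inconsistencies come with it: 9 of the 10 AEs of interest lie outside the section's own AE definition, and 1 of the 11 named serious risks, bone density loss, is in neither collected list.

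This rests on reading the AE sentence literally and counting terms as printed. How many events would be missed cannot be estimated, because the documents give no rate for unlisted events.

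A reader might also infer that the narrow definition governs who is discontinued under Section 5. The documents do not show this: the wording there is broader than Section 12 and does not refer to it. The two passages need to be reconciled, and no more than that is concluded here.

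The change should be made. It affects participant safety and costs little.

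**What to change.** In Section 12:

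- Replace the AE sentence with: *An AE is any untoward medical occurrence in a participant after enrolment, whether or not it is listed or considered related.* This also brings all AEs of interest inside the definition.
- Keep the Section 11 common reactions as solicited events.
- Add life-threatening and other important medical events to the SAE sentence.
- Add clinically recognised bone events (a fracture or a bone diagnosis, by participant report or chart) to the AEs of interest. No scan is needed.
- Collect these with one open-text question at the visits already planned.

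Reconcile the reference to other adverse events in Section 5 with the new definition, so that the wider wording does not alter the discontinuation rule by accident. No change to that rule is proposed here.

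The cost is protocol wording and one question per visit. There is no added visit, test or participant. The downside is small: more events to record and report.
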